4.4 Baseline Value

The baseline value of an assessment is defined as the last available measurement prior to the administration of study drug unless otherwise specified. For the matched analyses using Study 190-901, the baseline is the value at the matching assessment.

4.5 Visit Windows for Analysis

Clinical variables assessed at scheduled visits will be summarized by visit. Assessments will be classified to visit windows centered on the target scheduled visit study day. If more than one assessment falls within a window, the closest assessment to the target is selected for analysis. If two assessments are equally closest to the target, then the later assessment is selected. Details for the visit windows definition are provided in [Appendix 1](#).

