- If two subjects experience the same NCI CTCAE v. 4.0 Grade 3 AE, or if one subject has a Grade 4 AE that, in the investigator's opinion, is not related to the underlying disease, the BioMarin medical monitor will consult the DRB to evaluate the risk/benefit of continuing the study.

Another possible AE is infection from or failure of the indwelling ICV catheter. If an infection is suspected, blood and CSF samples will be drawn for assessment. The subsequent course of therapy, which is guided by site neurosurgical standards of care, may include antibiotic therapy, catheter reposition, or catheter withdrawal. If BMN 190 treatment is suspended, BMN 190 may resume if no more than 4 consecutive missed doses elapse after the last given dose.

If BMN 190 treatment is suspended for any reason, study participation may resume if no more than 4 consecutive doses were missed from the prior given dose.

If two or more subjects experience unacceptable drug-related toxicity, BioMarin may suspend further enrollment in the study pending a review of the data and upon consultation with the DRB. Depending on the nature and severity of the unacceptable drug-related toxicity, dosing of subjects already enrolled in the study may be continued or suspended pending further review. BioMarin will consult the DRB to aid in evaluating the risks of continuing the study and options for modification of the study to minimize subject risk.

Subjects who have a loss of 3 or more points on the combined motor and language components of the Hamburg CLN2 rating scale in any 1 year period may be discontinued at the discretion of the Investigator.

Subjects with a score of 0 on the combined motor and language components of the Hamburg CLN2 rating scale at two consecutive visits will be discontinued from treatment.

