14.4 Safety Analysis

Safety analysis will be descriptive.

All AEs will be coded by BioMarin using the current version of MedDRA to assign system organ class and preferred term classification to events and diseases, based on the original terms entered on the CRF. The incidence of AEs will be summarized by system organ class, preferred term, relationship to study treatment, and severity.

Concomitant medications will be coded using World Health Organization Drug Dictionary and summarized.

BIOMARIN¹⁹⁰⁻²⁰³ Amendment 6

Clinical laboratory data will be summarized in terms of observed values and changes from Baseline. Lab data will also be summarized relative to categorical reference ranges (e.g., lab normal ranges and/or CTCAE grade).

Vital signs will be summarized in terms of observed values and changes from Baseline.

ECGs will be summarized in terms of investigator overall interpretation, abnormal findings, and quantitative intervals (QTcF, etc.).

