14.2 Clinical Laboratory Tests

Clinical laboratory tests include chemistry, hematology, and urinalysis. Clinical laboratory test values and change from Baseline will be summarized descriptively by visit. Laboratory test values will be presented over time using boxplots.

Laboratory tests will also be summarized in terms of results relative to the lab reference ranges (low, high). Shift tables cross-tabulating the normal/abnormal results at Baseline vs. post-baseline visits will be provided as well. A supportive listing of abnormal test values will be produced.

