14.8 Cerebrospinal Fluid Surveillance (CSF)

Samples of standard clinical laboratory CSF for routine surveillance (cell count with differential, protein, glucose, and culture) will be summarized in a similar manner to clinical lab tests.

	BMN 190-203 Statistical Analysis Plan, Version 2.0	Pg. 43 of 53
---	---	--------------

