	Week 151	1058	Day 1024 and later
Blood for disease-related biomarkers i=1,2,3,4 j=1,2,3,4,5,6	Baseline	1	Pre-dose
	Week 9	57	[1, 85]
	Week 9 + i*8	57 + i*56	[30+i*56, 85+i*56]
	Week 49	337	[310, 379]
	Week 61	421	[380, 463]
	Week 61 + j*12	421 + j*84	[380+j*84, 463+j*84]
	Week 145	1016	Day 968 and later
EEG, standard awake, Optical coherence tomography, i=1,2,3,4	Baseline	<1	<=1
	Week 25	169	[2, 253]
	Week 25 + i*24	169 + i*168	[86+i*168, 253+i*168]
	Week 145	1016	Day 926 and later
	Week 145	1016	Day 926 and later
Height and weight assessments i=1,2,..4	Baseline	<1	<=1
	Week 25	169	[2, 253]
	Week 25 + i*24	169 + i*168	[86+i*168, 253+i*168]
	Week 145	1016	[926, 1092]
	Week 169		Day 1093 and later
Ophthalmologic assessments	Baseline	1	<=1
	Week 49	337	[2, 505]
	Week 97	673	[506, 841]
	Week 145	1016	Day 842 and later
Complete physical examination	Baseline	1	<=1
	Week 49	337	[2, 505]
	Week 97	673	[506, 841]
	Week 145	1016	[842, 1092]

BMN 190-203 Statistical Analysis Plan, Version 2.0

Pg. 48 of 53

	Week 169		Day 1093 and later
Blood/urine for clinical lab tests i=1,2,3 j=1,2,3,...6	Baseline	<=1	<=1
	Day 2	2	2
	Week 5	29	[3, 43]
	Week 9	57	[44, 71]
	Week 17	113	[72, 141]
	Week 17 + i*8	113 + i*56	[86+i*56, 141+i*56]
	Week 49	337	[310, 379]
	Week 61	421	[380, 463]
	Week 61 + j*12	421 + j*84	[380+j*84, 463+j*84]
	Week 145	1016	[968, 1092]
	Week 169		Day 1093 and later

*: only motor, language and motor-language scores will be summarized for screening visit.

**: In patients with present or past bradycardia, conduction disorders, or with structural heart disease, ECG will be performed within 30 minutes before the start of infusion (± 5 minutes), at 2 hours (± 15 minutes) during infusion, 30 (± 5) minutes after infusion end, and 12 hours (± 3 hours) after infusion end. In this case, please use the prior infusion assessment on Day 1 as baseline.

6-month Safety follow-up (Week 169) is defined using the window week of 156 to infinite.

BIOMARIN®	BMN 190-203 Statistical Analysis Plan, Version 2.0	Pg. 49 of 53
------------------	---	--------------

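### Blood and CSF by-visit and shift tables keep the record nearest the target day whatever its value, and no worst post-baseline summary is planned beside them

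*SAP*

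**What the plan says.** SAP 4.5 sets the rule for by-visit data. It opens: "Clinical variables assessed at scheduled visits will be summarized by visit". For a window holding several records: "If more than one assessment falls within a window, the closest assessment to the target is selected for analysis". For ties: "If two assessments are equally closest to the target, then the later assessment is selected". The rule takes no account of the value and does not mention unscheduled samples. The windows are in SAP Appendix 1.

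For blood and urine tests, SAP 14.2 plans values and changes by visit, boxplots over time, a low/high summary against reference ranges, and a listing of abnormal values. It adds: "Shift tables cross-tabulating the normal/abnormal results at Baseline vs. post-baseline visits will be provided as well". SAP 14.8 says that routine CSF surveillance samples "will be summarized in a similar manner to clinical lab tests"; it does not say where CSF taken for cause belongs.

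The protocol creates samples outside the schedule. Section 9.3.3.1: "If an infection is suspected, blood and CSF samples will be drawn for assessment". Section 9.7.3.3 requires clinically significant abnormal results to be repeated until explained or resolved, and 9.7.3.5 allows extra blood after certain adverse events. Protocol 14.4 says of categories: "Lab data will also be summarized relative to categorical reference ranges (e.g., lab normal ranges and/or CTCAE grade".

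**The concern.** A safety table of laboratory values should let the reader find the extremes. A rule that selects by distance from a target day tends to keep the routine sample and set aside the one taken because a child was unwell. It can also work in the other direction, when a repeat that has returned to normal lies nearer the target than the abnormal result that prompted it.

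Elsewhere the SAP avoids this. Vital signs use the maximum and minimum at each visit (14.3), and the ECG section counts children with one or more abnormal tracings (14.4). CSF, which is sampled at every infusion partly to watch for a device infection that the protocol names as a risk, has no equivalent. SAP Appendix 3 allows for at most 14 treated children in the matching, so one displaced value can matter to how a table reads.

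**Working it through.** The plan gives no figure to reproduce. The check is to rebuild the windows and apply the rule.

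**Inputs (SAP Appendix 1 and SAP 3.4)**
- CSF, Week 3 + 2i: target day 15 + 14i, window 9 + 14i to 22 + 14i. Offsets are −6 to +7 days, so the window is 14 days wide. The next window starts at 9 + 14(i + 1) = 23 + 14i, so there is no gap.
- Blood and urine, Week 17 + 8i: target 113 + 56i, window 86 + 56i to 141 + 56i. Offsets are −27 to +28, 56 days.
- Blood and urine, Week 61 + 12j: target 421 + 84j, window "380+j*84, 463+j*84". Offsets are −41 to +42, 84 days.
- Scheduled visits may fall within ±3 days of target.

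**Assumptions (not in the documents).** Each window holds one scheduled sample, with offset uniform over −3 to +3, and one unscheduled sample, uniform over the other days. Unscheduled samples are assigned to windows like any other record.

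**Days on which the unscheduled sample is selected** (nearer the target, or tied and later)

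| Scheduled offset | Winning offsets | Count |
|---|---|---|
| −3 | −2 to +3 | 6 |
| −2 | −1 to +2 | 4 |
| −1 | 0, +1 | 2 |
| 0 | none | 0 |
| +1 | 0 | 1 |
| +2 | −1 to +1 | 3 |
| +3 | −2 to +2 | 5 |

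The counts sum to 21 over seven offsets. They are the same for all three windows, because every winning day lies within 3 days of target.

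**Average share selected = 21 / (7 × (width − 1))**
- CSF: 21 / (7 × 13) = 23.1% selected, 76.9% displaced. By scheduled offset, displacement runs from 7/13 (54%) to 13/13 (100%).
- 56-day blood window: 21 / (7 × 55) = 5.5% selected, 94.5% displaced (49/55, or 89%, to 100%).
- 84-day blood window: 21 / (7 × 83) = 3.6% selected, 96.4% displaced (77/83, or 93%, to 100%).

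**A repeat replacing an abnormal scheduled result.** The first three rows give this directly. If the scheduled sample was 3 days early, a repeat on any of the next 6 days is selected instead. If it was 2 days early, the next 4 days; if 1 day early, the next 2. If it was on or after target, a later repeat never displaces it.

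**Last CSF window.** The percentages leave this window out. It is open from Day 1003, so all later CSF from a child reduces to one record. Its target is Day 1016, although the 14-day pattern gives 15 + 14 × 71 = 1009. A scheduled sample on Day 1009 would lose to any sample on Days 1010 to 1023.

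**The case against.** The case for leaving the SAP alone has real strength.

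- The low/high summary in SAP 14.2 is not said to be by visit or limited to selected records, and 14.8 carries the same outputs over to CSF. It may already include every result. Abnormal values are also listed, and in so small a study a listing can be read child by child.
- Infection is counted in the adverse event tables. SAP 14.1.7 summarises meningitis and device-related events, with no window selection, and protocol 9.7.3.3 makes each clinically significant laboratory result after Screening an adverse event.
- The displacement is weakest when infection interrupts treatment. Scheduled CSF is taken just before an infusion. If that infusion is missed, a sample taken for cause has no competitor and is selected. After device replacement the next infusion is at least 14 days after surgery (protocol 9.1).

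All of this stands, and it rules out two stronger readings that a reader might infer: that the worst values reach no summary at all, and that the plan understates infection. It does not close the gap. The record set for the low/high summary is left open, a listing is not a summary, and adverse event tables give terms and grades rather than cell counts, protein, glucose or culture results.

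A reader might also take the missing CTCAE-grade table as a lost commitment. It is not: the protocol offers grade only as an example, with and/or, and the SAP uses normal ranges.

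Finally, protocol 7.2 reports device infections in 2 of 24 children. At that rate 14 children would give 14 × 2/24 = 1.2 expected, and 1 − (22/24)^14 = 70% for at least one. That is the chance of an infection, borrowed from another study. It is not the chance that a between-visit sample exists and is displaced, so it cannot show that values are likely to be lost.

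**Conclusion.** The point holds for the by-visit tables, and for the shift tables in so far as these use visit-selected records, as their wording suggests. Their records are chosen by timing, and no table based on the worst post-baseline value is planned for blood or CSF. Between-visit results are usually displaced: about 77% of the time for CSF and 95% to 96% for the two wider blood windows. Those figures rest on uniform timing, a scheduled sample being present, and unscheduled samples being windowed. A missed visit reverses the result for that window. If unscheduled samples are not windowed at all, none of them reaches the by-visit tables.

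This is a weakness in how laboratory safety is displayed, not evidence that infections go uncounted. It is worth correcting because the remedy is standard and cheap, and because silence on unscheduled records leaves the choice to be made after the data are seen.

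**What to change.** In SAP 14.2 and 14.8:

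- State that the low/high reference-range summary uses all post-baseline results, scheduled and unscheduled.
- For blood tests, add a shift table from baseline to worst post-baseline category.
- For CSF, add the number of children with any post-baseline cell count, protein or glucose outside the reference range, or any positive culture, flagged as routine or for cause where this is recorded.
- Keep the windowed by-visit tables as they are.

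The cost is SAP wording and two descriptive tables from data already collected, with no change to trial procedures. The extreme-value counts will look slightly less favourable than the by-visit tables, and the text should say that they pool all samples, including those drawn for cause.

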4.6 Handling of Dropouts and Missing Data

Missing ML assessments for symptomatic patients (baseline ML < 6 points) will not have much impact on the assessment of the primary endpoint since the disease progression on ML score is close to linear, estimation of rate of decline in ML is reliable for follow-up periods of greater than 6 months and all subjects had been followed > 6 months. Impact of missing ML assessments for asymptomatic subjects (baseline ML = 6 points) is also expected to be low since the follow-up of matched Study 190-901 subjects is limited to the length of follow-up of the Study 190-203 subject matched. Additional analyses will be conducted as appropriate to evaluate the impact of the COVID-19 pandemic on the study conduct and results, especially for the treatment effect as estimated in the trial.

BIOMARIN®	BMN 190-203 Statistical Analysis Plan, Version 2.0	Pg. 17 of 53
------------------	---	--------------

Statistical models for time-to-event analyses accommodate variable follow-up arising from staggered accrual or early study discontinuation, using an assumption of missing at random.

The CLN2 assessment schedule for Study 190-901 is not regular and does not generally match CLN2 assessment frequency in Study 190-203. Summaries of CLN2 score over a window grid would have highly variable N which is difficult to interpret. For this reason, interpolation will be used. Summaries of matched Study 190-203 and Study 190-901 CLN2 data will be based on data that has been imputed to the Study 203 visit target, using linear interpolation between Study 190-901 subject visits. Details are provided in [Appendix 4](#).

Partial or missing dates for adverse events and medications will be imputed conservatively by assignment to the earliest and latest possible dates for start and stop dates, respectively.

Some patients only have year of birth recorded as permitted by the site Institutional Review Board. Age in integer months is provided at each visit for Denver assessment. For subjects with incomplete date of birth provided, the date of birth will be imputed by back-calculation of birth date from the date of Denver assessment: (date of Denver) – round ((age in months) x (365.25/12)). For subjects with multiple Denver assessments, the average of the imputed date of births is used.

BIOMARIN®	BMN 190-203 Statistical Analysis Plan, Version 2.0	Pg. 18 of 53
------------------	---	--------------

5 SUBJECT DISPOSITION

The following will be summarized:

- Number of subjects enrolled
- Number of subjects who did not fulfill all inclusion/exclusion criteria
- Number of subjects who received study drug
- Length of time on study

Draft

	BMN 190-203 Statistical Analysis Plan, Version 2.0	Pg. 19 of 53
---	---	--------------

6 DISCONTINUATION AND COMPLETION

For subjects who prematurely discontinued study, the primary reason for discontinuation will be summarized. A similar summary will be provided for subjects who discontinue study drug.

- Number of subjects who completed study
- Number of subjects who completed treatment
- Reason for study discontinuation
- Reason for treatment discontinuation

Draft

	BMN 190-203 Statistical Analysis Plan, Version 2.0	Pg. 20 of 53
---	---	--------------

7 PROTOCOL EXEMPTIONS AND DEVIATIONS

The Study 190-203 trial's guideline for managing protocol deviations defines protocol deviations, including whether they are minor or major. Major protocol deviations will be summarized for the ITT population. A data listing of protocol deviations will be provided as well.

Draft

BIOMARIN®	BMN 190-203 Statistical Analysis Plan, Version 2.0	Pg. 21 of 53
------------------	---	--------------

8 DEMOGRAPHICS AND BASELINE CHARACTERISTICS

Summaries of the following variables will be performed for the ITT population

- Age (years)
- Age group (<2, 2 - <3, \geq 3 years)
- Sex
- Ethnicity
- Race
- Height (cm)
- Weight (kg)
- CLN2 Motor scale score
- CLN2 Language scale score
- CLN2 Vision scale score
- CLN2 Seizure scale score
- CLN2 Motor-Language (ML) score
- CLN2 Motor-Language-Vision-Seizure (MLVS) score
- Age of diagnosis (years)
- Age of first symptoms (years)

	BMN 190-203 Statistical Analysis Plan, Version 2.0	Pg. 22 of 53
---	---	--------------

9 MEDICAL HISTORY

Medical history will be coded in accordance with the most current version of Medical Dictionary for Regulatory Activities (MedDRA) at the time of coding. Summaries will be by system organ class (SOC) and preferred term (PT).

Draft

BIOMARIN®	BMN 190-203 Statistical Analysis Plan, Version 2.0	Pg. 23 of 53
------------------	---	--------------

10 PRIOR AND CONCOMITANT MEDICATIONS/PROCEDURES

Prior and concomitant medications are defined as follows:

- Prior medication – any medication with a stop date prior to the date of the first infusion
- Concomitant medication – any medication delivered on or after the date of the first infusion.
 - Medication has start date on or after date of first infusion
 - Medication is listed as ‘continuing’
 - Medication has start date prior to the date of the first infusion and stop date on or after date of first infusion

All medications will be coded using the current version of the World Health Organization Drug (WHO Drug) Dictionary. Prior and concomitant medication use will be separately summarized by Anatomical Therapeutic Chemical (ATC) medication class (Level 4) and preferred name (i.e., generic medication name). A subject reporting the same medication more than once will be counted once when calculating the number and percentage of subject who received the medication.

BIOMARIN®	BMN 190-203 Statistical Analysis Plan, Version 2.0	Pg. 24 of 53
------------------	---	--------------

11 COMPLIANCE

Measures of compliance will be summarized:

Actual study drug intake relative to planned study drug intake, expressed as a proportion:

$$100\% \times \frac{\text{Exposure (mg)}}{\text{Planned intake (mg)}}$$

Number (%) of missed infusions

Number (%) of infusions administered more than 3 days outside the target dosing day.

Number (%) of interrupted infusions

BIOMARIN®	BMN 190-203 Statistical Analysis Plan, Version 2.0	Pg. 25 of 53
------------------	---	--------------

12 EXTENT OF EXPOSURE TO STUDY DRUG

Exposure to study drug will be summarized:

- Number of infusions
- Duration of dosing
- Exposure (mg)
- Total exposure over all infusions

Exposure (mg) will be calculated as follows:

$$\text{Exposure (mg)} = [\text{Volume (mL)}] \times [\text{Study drug concentration (mg/mL)}]$$

Draft

	BMN 190-203 Statistical Analysis Plan, Version 2.0	Pg. 26 of 53
---	---	--------------

13 EFFICACY EVALUATIONS

The efficacy analyses will be based on the ITT population. The PP population will be used for sensitivity analyses of the primary endpoint.

There will be two sets of efficacy analyses. The first set will be descriptive summaries of the Study 190-203 subjects at baseline and follow-up visits for all efficacy endpoints. The second set of analyses are for the CLN2 scales M, L, V, S, ML, MLV, and MLVS and based on matching Study 190-203 subjects to Study 190-901 historical controls. These will include descriptive summaries and statistical model results for treatment comparison to natural history. If natural history data are available on siblings with disease, data of sibling pairs will be presented in listings and graphical displays.

The primary efficacy endpoint is the rate of decline in the 0 to 6-point ML score and the primary analysis is based on matching with Study 190-901 subjects. All matched analyses will be based on a single matched set and the algorithm for matching has been prespecified prior to any matched analyses and is described in [Appendix 3](#). The matching will be a 3-1 matching of the Study 190-901 Evaluable population and the Study 190-203 ITT population. The matching criteria are:

- Equal ML score
- Age within 3 months
- Genome: equal number of common alleles (c.622C→T, c.509.1G→C)

For all matched analyses, Study 190-901 subjects will be weighted inversely to the number of Study 190-901 subjects matched to a given Study 190-203 subjects. The weights for 3, 2, and 1 Study 190-901 subject(s) matched to a given Study 190-203 subject will be 1/3, 1/2, and 1 respectively and the weights are normalized to the number of Study 190-901 subjects matched to Study 190-203 subjects.

To demonstrate comparability of the matched groups, summaries of the following variables will be produced for each group, with Study 190-901 subjects weighted according to number of matches.

- Age (years, continuous)
- Sex (Female/Male)
- Genome
- Site / Region
- M, L, ML, MLVS scale scores

	BMN 190-203 Statistical Analysis Plan, Version 2.0	Pg. 27 of 53
---	---	--------------

- Age of diagnosis (years)
- Age of first symptoms (years)

